2.1. Design and Participants

A randomized controlled trial (RCT) was conducted. The protocol was approved by the Institutional Review Board of Kaohsiung Medical University Hospital (reference numbers: KMUHIRB-SV(II)-20200071). All students provided informed consent before the participation.

A total of 23 students from the third grade of Department of Oral Hygiene students in Kaohsiung Medical University during the 2021 academic semester were recruited in the present study. Participants have to take both the courses of 'Basic Medical Nursing Care' and 'Oral Health Care for Community People and Long-term Care Residents' before intervention. Eleven students were randomized in the virtual-reality experimental group (EG) and 12 in the control group (CG).

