2.2. Randomization and Allocation

Students were randomly assigned to the virtual-reality experimental (EG) group and control group (CG). We used the random table from Excel with a ratio of 1:1 to accomplish the randomization. An open-label experimental design was used; students

were wise to the group they were allocated in.

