2.4.5 Covariates

Age and gender were assessed at baseline for each student in this study.

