2.5. Interventions

The VR-based training system (Pvix VR, EPED Inc.) equipped an optical portable wearable device that utilizes positioning motion recognition technology and a built-in virtual interactive software to assist in the self-training of future oral care personnel and health caregivers. Students are immersed in a 3D environment as soon as they put on the optical 3D glasses. The oral health interactive software stimulates diverse ability levels through the simulation of different actions. Students learn standard procedures of oral care through automatic assessment. In addition, the software customizes standard process courses and teaching plans in several fields.

The students in EG received VR-based training for elderly oral health care at 2-week (Time 2), 4-week (Time 3), and 6-week (Time 4) follow-ups. The learning module was divided into three sessions according to the physical condition (1) Mild disability, (2) Semi-disability, (3) Total disability and oral condition, (1) wearing dentures, (2) missing teeth of the elderly (Figure 2.). Students simulate the different physical and oral conditions of the elderly through virtual situations and provide suitable oral care methods. The whole training session took approximately two hours for each student; First, students were first given a short introduction to the VR system's use (10 minutes). Second, they were able to carry out oral care for the elderly while wearing VR goggles and using hand-controllers with the teaching and audio guides during the process (90 minutes), and an evaluation was taken after the intervention (20 minutes).

The students in CG do not receive any of the interventions. However, the same VR-based curriculum of oral health care on dependency elderly were provided at the end of the study.

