2.6. Data Collection

The students in both groups self-completed a baseline questionnaire after the allocation. The post-test was collected immediately after each intervention, and the satisfaction survey was collected at the end of the whole intervention in the experimental group. As for the control group, the post-test was collected at 2-week (Time 2), 4-week (Time 3), and 6-week (Time 4) follow-ups.

Statistical Analysis Plan

This study explored the variables' relationships using STATA version 13.1 (Stata Corp LP, College Station, Texas, USA). Percentage, Fisher's exact test, and Wilcoxon rank-sum test were used to compare the VRG and CG demographic variables. Wilcoxon rank-sum test compares the difference of oral care-related knowledge, Attitude, self-efficacy, and intention within groups. Linear regression in generalized estimating equations (GEE) compares the difference of oral care-related knowledge, attitude, self-efficacy, and intention between groups. The effect size (Cohen's d) of continuous variables were calculated from the mean difference between baseline and the follow-ups between the VRG and CG. An effect of 0.20 is small, 0.50 is medium, and 0.80 is large[16].

[figure not shown]

Figure 1. CONSORT flow diagram

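### The between-group GEE is unspecified for 23 students; ordinary large-sample inference would usually be too liberal, so name one contrast and a small-sample test for it

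*Combined protocol and SAP*

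**What the plan says.** On testing the outcomes between groups, the Statistical Analysis Plan has one clear sentence: "Linear regression in generalized estimating equations (GEE) compares the difference of oral care-related knowledge, attitude, self-efficacy, and intention between groups". The software is given as "using STATA version 13.1", with no command or variance option.

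Other statements bear on it:

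- **Size and visits.** Section 2.1 reports 11 students in the experimental group and 12 in the control group. Follow-up is "at 2-week (Time 2), 4-week (Time 3), and 6-week (Time 4) follow-ups" (section 2.5), so each student has a baseline and three post-tests.
- **Baseline.** "The students in both groups self-completed a baseline questionnaire after the allocation" (section 2.6). Section 2.2 adds: "An open-label experimental design was used".
- **Other use of baseline.** Cohen's d is "calculated from the mean difference between baseline and the follow-ups between the VRG and CG". No test or interval is attached to it.
- **Covariates.** "Age and gender were assessed at baseline for each student in this study" (section 2.4.5). The plan does not say whether they enter the GEE.
- **Rank-sum test.** The sentence before the GEE sentence applies the Wilcoxon rank-sum test to the same four outcomes but calls it a within-group comparison. Rank-sum compares two independent samples, so the label does not fit the test.

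No significance level, power calculation, expected SD or within-student correlation is given.

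**The concern.** GEE inference is justified when there are many independent units. Here the units are the 23 students; the 92 scores (23 x 4) do not change that. With so few, the ordinary sandwich variance is biased downwards and a normal or chi-square reference is too narrow. The p-values then tend to be too small and the intervals too short.

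The sentence also leaves open what is being tested: one visit, the average of the follow-ups, a joint test over visits, or change from baseline. These choices give materially different error rates and precision. Left open, they can be made after the results are visible, and they affect all four outcomes.

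**Working it through.** **Inputs.** From the documents: 11 v 12 students, baseline plus Times 2, 3 and 4. Assumed, because the documents are silent: two-sided 5% level, no dropout, normal scores, and within-student correlation rho of 0.3, 0.5 or 0.7, either exchangeable or AR(1). The plan has no figure of its own to reproduce.

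**Step 1: closed-form check of sandwich z.** With complete data and a group-by-time model, the uncorrected sandwich divides by n in each arm instead of n - 1. With about 11.5 per arm the variance is too small by 10.5/11.5 = 0.913. Rejecting at 1.96 is then like rejecting an ordinary t statistic on 21 df at 1.96 x sqrt(0.913) = 1.873, and P(|t21| > 1.873) = 7.5%. With the n/(n - 1) factor of 23/22 the cut-off is 1.915 and the rate is 6.9%.

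**Step 2: simulated null trials.** Unless noted, 40,000 trials per cell over the six correlation settings. Three mean models were used: baseline as a fourth repeated outcome, Times 2-4 only, and Times 2-4 with baseline as covariate.

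| Inference | Type I error |
|---|---|
| Sandwich z, Time 4 contrast | 6.7-8.3% |
| Sandwich z, average of Times 2-4, no baseline (exchangeable; 8,000-20,000 trials) | 7.2-7.7% |
| Sandwich z, average of Times 2-4, baseline as covariate (8,000-20,000 trials) | 8.4-9.3% |
| Sandwich chi-square, joint 3-df test | 11.3-13.7% |
| Model-based z, Time 4, correct exchangeable, residual-df scale | 4.5-5.8% |
| Model-based z, Time 4, correct exchangeable, divisor N | 6.5-7.2% |
| Model-based z, exchangeable working correlation, AR(1) 0.7 truth, baseline as repeated outcome | 11.0-13.7% |
| Model-based z, independence working correlation, Time 4 group-by-time term | 0.1-6.2% |
| Mancl-DeRouen variance, t(20), single contrast | 3.6-4.0% |
| Mancl-DeRouen variance, F(3,20), joint | 5.0-5.4% |
| Time 4 regression on group and baseline, t(20) | 4.8-5.1% |

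Adding age and gender to the baseline-adjusted averaged contrast raises sandwich z to 10.4-10.6%. On a bounded 0-20 score, sandwich z gives 7.2-8.2% at an assumed mean 15.7 and SD 3.2 (regression with t(20): 4.8-5.0%), and 7.4% at an assumed mean 15 and SD 2.5 (1,500 trials). The other three scales were not checked this way.

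**Step 3: what baseline adjustment buys.** Let r be the correlation between baseline and the analysed visit. Relative variances at n = 23 are (1 - r^2) x 20/19 adjusted, 1 follow-up-only, and 2(1 - r) for change scores.

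- Against change scores the ratio is (1 + r)/2 x 20/19, which is below 1 when r < 0.90.
- Against follow-up-only, (1 - r^2) x 20/19 is below 1 when r > sqrt(1/20) = 0.224.
- At r = 0.3 / 0.5 / 0.7 the ratio to follow-up-only is 0.958 / 0.789 / 0.537.
- Under AR(1), r at Time 4 is rho cubed = 0.027 / 0.125 / 0.343, and the ratio is 1.052 / 1.036 / 0.929. Adjustment then costs up to about 5% in two of the three cells.

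**Step 4: baseline completed after open allocation.** If knowing the allocation shifts baseline by d SD with no true effect, the bias is r x d adjusted, d in change scores and 0 follow-up-only. The documents give no d, so a range is shown. The adjusted SE is sqrt[(1 - r^2) x 20/19 x (1/11 + 1/12)]. At r = 0.7 it is sqrt(0.51 x 1.0526 x 0.1742) = 0.306 SD. For d = 0.2 the non-centrality is 0.14/0.306 = 0.46, which gives about 7.2% on t(20). The other cells follow in the same way.

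| Assumed d | Adjusted bias in SD, r = 0.3 / 0.5 / 0.7 | Adjusted type I error |
|---|---|---|
| 0.1 | 0.03 / 0.05 / 0.07 | 5.1 / 5.2 / 5.6% |
| 0.2 | 0.06 / 0.10 / 0.14 | 5.2 / 5.8 / 7.2% |
| 0.4 | 0.12 / 0.20 / 0.28 | 5.9 / 8.1 / 14.1% |

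Simulation at d = 0.2 gives 5.2 / 5.8 / 7.1% adjusted, 6.7 / 7.5 / 9.0% for change scores and about 5% follow-up-only.

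**Step 5: power for an assumed 1.0 SD effect at Time 4.** Values are for rho = 0.3 / 0.5 / 0.7.

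| Analysis | Exchangeable | AR(1) |
|---|---|---|
| Adjusted regression, t(20) | 64 / 73 / 88% | 61 / 61 / 66% |
| Mancl-DeRouen GEE, t(20) | 61 / 69 / 85% | 57 / 56 / 61% |
| Follow-up-only t-test | 63% | 63% |

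**The case against.** The strongest reply is that the plan never names a sandwich variance, a z reference or a 5% level. A reader might infer that the planned test has a 7-8% error rate. The documents do not support that: one permitted choice, model-based z with a residual-df scale and the correct correlation, runs at 4.5-5.8%, and an independence working correlation can even be conservative. This part of the objection stands, and every rate above is conditional. What survives it is that most ordinary large-sample choices are too liberal at this size and the plan excludes none of them.

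A reader might also infer that the plan rejects baseline adjustment. It does not; it is silent on baseline in the GEE.

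Third, if the within-group label on the rank-sum test is a slip, the plan holds a second between-group test that does not rest on GEE theory. The text does not settle this. The GEE is therefore the only clearly stated between-group outcome test, not certainly the only one.

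Finally, it is tempting to make baseline adjustment the obvious main analysis. Steps 3 and 4 do not support that without a judgement that r exceeds about 0.22 and that any shift from knowing the allocation is small. The documents give neither quantity.

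**Conclusion.** The concern holds as under-specification with a foreseeable consequence. For 11 v 12 students, the only clearly stated between-group outcome test has no small-sample inference, variance estimator, reference distribution, contrast or handling of baseline. At an assumed two-sided 5% level, with normal complete data and rho of 0.3 to 0.7, ordinary large-sample inference usually rejects too often. Sandwich z gives about 7-8% for a single visit, somewhat more for a baseline-adjusted average, and about 11-14% for a joint test. Model-based z gives about 5-7% when an exchangeable correlation is right and up to about 14% when correlation decays. The inflation per single-visit test is moderate, but it bears on all four outcomes. The case for adjusting for baseline is real but conditional, and is weakened by when baseline was collected. This should be corrected; it does not invalidate the design.

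**What to change.** In the Statistical Analysis Plan:

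1. Name one target contrast for each outcome, for example the Time 4 group difference, and state the significance level.
2. Test it by ordinary linear regression with a t reference whose df come from students, and report the difference with its 95% CI.
3. Report it both adjusted for that outcome's baseline score (t(20), from 23 - 3) and follow-up-only (t(21), from 23 - 2), and name which is main. State as a limitation that baseline followed open-label allocation, so the adjusted estimate can carry a bias of r times any baseline shift.
4. If the GEE is kept to describe all visits, give its terms and working correlation, and use a Mancl-DeRouen variance with t or F on student-level df, for example t(20) and F(3,20).
5. Say whether age and gender enter; together they cost 2 df.
6. Clarify the rank-sum sentence: correct either the test or the within-group label.
7. If the outcome data have already been seen, label the analysis post hoc. Section 2.1 is in the past tense and already reports the allocation, so the documents do not show that this choice can still be made in advance.

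**Cost.** SAP wording and a little code; no new data. The regression needs no special software; the documents do not show whether the named Stata version offers the corrected GEE variance. Corrected GEE intervals are about 17-20% wider than uncorrected robust ones, its single-contrast test is slightly conservative, and its power is below the follow-up-only t-test in four of the six cells in Step 5. Adjustment loses up to about 5% precision against follow-up-only if r is below about 0.22.

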2.3. Instrument

A structured questionnaire related to elderly oral health was developed to collect data on five parts: (1) demographics (i.e., gender, age), (2) oral care-related knowledge, (3) attitude toward oral care, (4) self-efficacy toward oral care (5) intention to oral care behaviors. A panel of experts reviewed items to assess content validity. The content validity index was 0.97-1.00. The reliability of each scale was assessed in terms of internal consistency (Cronbach's alpha coefficient). The satisfaction survey was based on System Usability Scale (SUS) to measure the usability of the VR-based learning system the students used during the oral care training. The SUS covered the effectiveness (the ability of users to complete tasks using the system, and the quality of the output of those tasks), efficiency (the level of resource consumed in performing tasks), and satisfaction (users' subjective reactions to using the system) [15].

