2.4. Outcome Measures

2.4.1. Elderly oral care-related knowledge

Twenty items measured elderly oral care-related knowledge; for example, 'There is no need to consider the size of the interdental brush.' Possible responses included True (1), False (0), and I do not know (0), with possible scores ranged from 0 to 20; a higher score indicated a higher degree of oral-care-related knowledge. The KR-20 coefficient was 0.56 for this scale.

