2.4.2. Attitude toward elderly oral care

Seven items measured attitude toward elderly oral care, for example, 'Assist disabled elderly to clean their teeth is annoying.' Each item was scored on a five-point Likert-type scale ranging from 1 (strongly disagree) to 5 (strongly agree). Possible scores ranged from 5 to 35; a higher score indicated a more positive attitude toward oral care for the elderly. Cronbach's alpha was 0.70 for this scale.

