2.4.3 Self-efficacy of elderly oral care

Eleven items were used to evaluate the self-efficacy of elderly oral care. Students indicated their degrees of agreement with statements related to perceptions of personal ability concerning oral care for the elderly. For example, 'I am confident to remind disabled elderly having regular dental visits every six months.' Each item was scored on a five-point Likert-type scale ranging from 1 (strongly disagree) to 5 (strongly agree). Possible scores ranged from 5 to 55; a higher score indicated more substantial confidence toward oral care for the elderly. Cronbach's alpha was 0.87 for this scale.

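### Cohen's d is built on raw change from baseline with no stated SD; a baseline-adjusted difference would be more precise and would not move with a chance baseline gap

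*Combined protocol and SAP*

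**What the plan says.** The Statistical Analysis Plan (after section 2.6) compares knowledge, attitude, self-efficacy and intention between arms by linear regression in GEE. It then adds an effect size for the continuous variables, "calculated from the mean difference between baseline and the follow-ups between the VRG and CG", and reads it against one set of benchmarks: "An effect of 0.20 is small, 0.50 is medium, and 0.80 is large". It does not say which SD standardises the difference, and it mentions baseline adjustment neither for d nor for the GEE.

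Section 2.1 puts 11 students in the VR arm and 12 in the control arm. Section 2.2 describes simple allocation "with a ratio of 1:1 to accomplish the randomization", open-label. Section 2.6 places the baseline questionnaire after allocation, with follow-up at 2, 4 and 6 weeks. For the knowledge scale, section 2.4.1 reports: "The KR-20 coefficient was 0.56 for this scale". No test-retest reliability or baseline-to-follow-up correlation is given for any scale.

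**The concern.** Subtracting the whole baseline score is the best use of it only when baseline and follow-up are almost perfectly correlated. Otherwise subtraction over-corrects: it carries baseline noise into the outcome, and an arm that starts low by chance tends to show a larger gain without any VR effect. With 23 students, sizeable chance gaps are to be expected. A d that depends partly on where the arms happened to start can cross a benchmark for that reason alone. The unstated SD adds to this, because the same difference in scale points gives different values of d under different divisors.

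**Working it through.** The plan reports no power calculation, SD or value of d, so there is no figure of its own to reproduce.

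**Inputs.** Arm sizes 11 and 12 (section 2.1). Assumptions: equal score SD at both visits (set to 1), normally distributed scores, and r from 0.3 to 0.8. The value 0.56 is included as a rough guide for knowledge, borrowed from the KR-20 in section 2.4.1.

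**Step 1, chance baseline gap.** SE = √(1/11 + 1/12) = 0.417 SD, so 95% of gaps lie within ±1.96 × 0.417 = ±0.82 SD. P(|gap| > 0.5 SD) = P(|Z| > 0.5/0.417) = 0.23.

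**Step 2, variance.** Per student, raw change has variance 2(1 − r); the baseline-adjusted outcome has 1 − r². Their ratio is 2/(1 + r), which exceeds 1 whenever r is below 1.

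**Step 3, cost of the slope.** With N = 23 and two arms, estimating one common slope inflates the adjusted variance on average by 1/(N − 4) = 1/19, about 5%. The net ratio is [2/(1 + r)] ÷ (20/19) = 1.9/(1 + r). Adjustment therefore still wins for r below 0.9.

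**Step 4, shift from a gap.** With no VR effect, a baseline gap g moves the expected change difference by (1 − r) × g in the opposite direction. Here g = 0.5 SD.

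| r | Change, 2(1 − r) | Adjusted, 1 − r² | Excess variance of change | Excess net of slope cost | Shift at 0.5 SD gap |
|---|---|---|---|---|---|
| 0.3 | 1.40 | 0.91 | 54% | 46% | 0.35 SD |
| 0.4 | 1.20 | 0.84 | 43% | 36% | 0.30 SD |
| 0.56 | 0.88 | 0.69 | 28% | 22% | 0.22 SD |
| 0.7 | 0.60 | 0.51 | 18% | 12% | 0.15 SD |
| 0.8 | 0.40 | 0.36 | 11% | 6% | 0.10 SD |

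In 100,000 simulated null trials for each of r = 0.3, 0.56, 0.7 and 0.87, the mean d from change scores was 0.00. The shift is conditional on the observed gap and is not an average bias.

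**Step 5, effect on d.** At r = 0.56, scaled on a single-visit SD, the SE of d is √0.88 × 0.417 = 0.39 from change and √0.686 × 0.417 = 0.35 from adjustment (slope taken as known). With no VR effect, the normal-approximation chance of |d| ≥ 0.50 is about 20% v 15%.

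**Step 6, the divisor.** A difference of 0.50 on the single-visit SD becomes 0.50/√(2(1 − r)) on the SD of change: 0.50/√1.40 = 0.42 at r = 0.3, 0.50/√0.88 = 0.53 at r = 0.56, and 0.50/√0.40 = 0.79 at r = 0.8. The benchmark reached can depend on a choice the plan does not state.

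**The case against.** The strongest reply is that little rests on d. The between-group comparison is the GEE, and no success criterion or sample size uses the effect size. Moreover, most of the instability in d comes from having 23 students: step 5 shows only a modest gain. Both points stand, and they limit the consequence. They do not favour raw change, since adjustment uses data already collected and is more precise over the whole range examined.

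A reader might infer from the KR-20 of 0.56 that r for knowledge cannot exceed 0.56. The documents do not support that. KR-20 measures internal consistency, and repeated items over 2 to 6 weeks can share stable item-specific variance that raises r above it. Hence the range runs up to 0.8, where the shift from a 0.5 SD gap is 0.10 SD; it falls below the 0.20 benchmark once r passes 0.6.

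A reader might also infer, from the unequal reliabilities (0.56, 0.70 and 0.87 for knowledge, attitude and self-efficacy), that the labels mislead when outcomes are compared. The plan does not say it will rank or compare outcomes by label. How far reliability attenuates d depends on the unstated divisor, and no coefficient is given for intention. That reading is not pursued here.

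Lastly, baseline was completed after students knew their arm, so a gap need not be pure chance. This stands, and it applies to change scores and adjustment alike.

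**Conclusion.** The point holds as an inexpensive improvement to how the effect size is defined. Raw change is less precise than a baseline-adjusted difference at any r below 1 before the slope is estimated, and below 0.9 after it. The excess variance is 54% to 11% over r = 0.3 to 0.8, against a slope cost of about 5%. In a given allocation, a 0.5 SD baseline gap moves the change difference by 0.35 to 0.10 SD. These sizes rest on the assumed r, equal SDs at both visits, and a gap due to chance.

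It would go too far to call d biased, since the shift averages to zero over randomisations, or to conclude that the GEE test is invalid. The documents establish neither.

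**What to change.** Derive each d from the baseline-adjusted difference between arms at each follow-up: either regress the follow-up score on arm and baseline score, or fit the GEE to the follow-up scores with baseline as a covariate. Divide by one SD named in the plan, such as the pooled baseline SD, for every outcome and visit. Report the adjusted difference in scale points beside d (for example, knowledge items out of 20).

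The cost is one extra coefficient per model and a few table columns, with no new data collection. State as a limitation that baseline was self-completed after open-label allocation, so any influence of known allocation on baseline answers is not fully repaired by either method.

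### Cohen's d from 11 and 12 students has no stated small-sample correction: about 3.8% too large on average, a small bias that Hedges' g would remove at no cost

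*Combined protocol and SAP*

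**What the plan says.** The Statistical Analysis Plan section defines the standardised effect in one sentence: "The effect size (Cohen's d) of continuous variables were calculated from the mean difference between baseline and the follow-ups", comparing the VR group with the control group. The next sentence gives the only rule for judging its size: "An effect of 0.20 is small, 0.50 is medium, and 0.80 is large". The section gives no formula for d. It does not say which SD is the denominator, mentions no small-sample correction and plans no interval for d.

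Section 2.1 gives the numbers: "A total of 23 students from the third grade", split 11 to the VR group and 12 to control. Four outcomes are compared between groups, and section 2.6 sets three follow-ups (weeks 2, 4 and 6), so up to 4 × 3 = 12 values of d could be reported. The between-group comparison itself is made by GEE regression. Nothing in the plan makes a test, sample size or decision depend on d.

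**The concern.** In small samples Cohen's d is biased away from zero, because the sample SD in its denominator is itself estimated with error. The size of the bias depends only on the degrees of freedom of that SD, so it is known in advance and can be removed. Naming the SD or adding an interval would not remove it from the point estimate.

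It deserves a line here because the groups are very small and because the plan states no target difference or margin. The three size words are all a reader has for judging how large an effect is. A d printed just above a cut-off would carry a label that its bias-corrected value does not reach.

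**Working it through.** The plan states no bias, power or sample-size figure, so there is nothing to reproduce first.

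**Inputs.** Group sizes 11 and 12 (section 2.1); cut-offs 0.20, 0.50 and 0.80 (Statistical Analysis Plan). Assumed, because the plan does not say: pooled SD, normal data, no missing students. Then df = 11 + 12 − 2 = 21.

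**Step 1: the bias factor.** The expected value of d is δ/J, where δ is the true effect and J = Γ(df/2) / [√(df/2) × Γ((df − 1)/2)].

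- Exact: J(21) = 0.9638, so 1/J = 1.0376, or 3.8% away from zero.
- Approximate: J = 1 − 3/(4 × 21 − 1) = 1 − 3/83 = 0.9639, which agrees.
- Control-group SD, df = 12 − 1 = 11: J = 0.930, 1/J = 1.075, or 7.5%.
- Fewer students at a visit, pooled SD: 4.0% at 20 df and 4.4% at 18 df.

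**Step 2: the bias against sampling error.** With k² = 1/11 + 1/12 = 0.1742, Var(d) = (21/19)(k² + δ²) − (δ/J)². The mean squared error (MSE) of d is Var(d) + bias². For g = J × d the mean bias is zero and the MSE is J² × Var(d), with J² = 0.929.

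| True effect | Mean of d | Bias | SD of d | MSE of d | MSE of g | Reduction |
|---|---|---|---|---|---|---|
| 0.2 | 0.208 | 0.008 | 0.440 | 0.194 | 0.180 | 7.1% |
| 0.5 | 0.519 | 0.019 | 0.447 | 0.200 | 0.186 | 7.3% |
| 0.8 | 0.830 | 0.030 | 0.459 | 0.212 | 0.196 | 7.5% |

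The bias is about 2% to 7% of one SD of d. The 95% confidence interval is about −0.34 to 1.33 around an observed d of 0.50, and about −0.06 to 1.64 around 0.80.

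**Step 3: where a label can change.** A label drops a step only if d lies between a cut-off c and c/J: 0.200–0.208, 0.500–0.519 or 0.800–0.830.

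**Step 4: whether the labels become more accurate.** This is the probability, from the noncentral t distribution, that the label (applied to the absolute value) matches that of the true effect.

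| True effect | Correct with d | Correct with g |
|---|---|---|
| 0.3 | 0.359 | 0.367 |
| 0.5 | 0.261 | 0.264 |
| 0.65 | 0.273 | 0.281 |
| 0.8 | 0.509 | 0.482 |
| 1.0 | 0.685 | 0.660 |

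Correction gains about one percentage point at most for true effects of 0.1 to 0.7, and loses 2 to 3 points for 0.8 to 1.0.

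**The case against.** The strongest reply is that the bias is immaterial. It is a few hundredths at most, beside an interval more than 1.6 units wide, and d is descriptive here. The unnamed SD and the missing interval are larger weaknesses of the same sentence; the choice of SD alone moves the bias from 3.8% to 7.5%. All of that stands, and it keeps the point minor. It does not remove the case for correcting, because J below 1 reduces variance as well as bias, so nothing is given up in precision.

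Four stronger readings are tempting and are not supported.

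- **That every effect is overstated.** The 3.8% is a bias in the mean. The chance that d exceeds the true effect is 0.502, 0.506 and 0.509 at true effects of 0.2, 0.5 and 0.8, so about half of estimates fall below it.
- **That the bias always favours VR.** It acts away from zero. It vanishes when the true effect is zero and exaggerates an unfavourable effect just as it does a favourable one.
- **That some effects are labelled one step too large.** The documents contain no results, so it is unknown whether any d falls in the narrow bands. Correction would change a single label with probability 4.0%, 4.7% and 4.4% at true effects of 0.2, 0.5 and 0.8. With 12 values and an assumed correlation of 0.5, the chance of at least one change is roughly 33% to 44%. These figures count labels that move, not labels that were wrong; step 4 shows no overall gain in accuracy. The documents give no correlation either.
- **That the plan specifies an uncorrected d.** This is inferred from the name of the measure and the silence on correction. If a correction is already applied, one clarifying sentence closes that part.

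**Conclusion.** The point holds as a minor one. As written, the plan uses a d with no stated small-sample correction whose expected value is about 3.8% too far from zero with a pooled SD, or about 7.5% with the control-group SD. These figures assume normal data and complete follow-up. The absolute bias is 0.008 to 0.030 for true effects of 0.2 to 0.8, well inside sampling error.

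The gain from correcting is an estimator without mean bias and with about 7% lower mean squared error. More accurate size labels are not part of the gain, and no mislabelling rate should be quoted. The GEE comparison is unaffected.

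**What to change.** Amend the effect-size sentence in the Statistical Analysis Plan to:

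1. name the standardising SD (for example, the pooled SD of the change scores);
2. report Hedges' g = J × d, with J = 1 − 3/(4 × df − 1), which is 0.964 at 21 df, using the actual df at each visit and for the SD chosen;
3. give a 95% confidence interval with each g;
4. base any size label on g together with its interval, not on the point estimate alone.

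The cost is one sentence in the plan, one multiplication per value and the calculation of the intervals. With a pooled SD and complete data each reported effect becomes about 3.6% smaller (1 − 0.964). No new data are needed.
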